### **8.3 Study Discontinuation**

Subjects will remain in the study through at least Study Day 15 (or longer if needed to follow up study drug-related adverse events). Mortality is assessed via a phone call or other digital media at Day 29.

After treatment, participants will be monitored through at least Study Day 15 (or longer if needed to follow study drug-related AEs/SAEs). Participants may discontinue from the study by withdrawing consent at any time or for any reason as presented in [Section 9.7](#).

### **8.5 Concomitant Medication/Treatment**

Record the name, start/stop date, indication for use, route, and whether ongoing or stopped for medications/treatments taken within two weeks prior to study entry as well as any medications taken during the study are to be recorded. The use of other DHODH inhibitors is not permitted during the study including leflunomide or teriflunomide (see [Section 8.8](#)).

PROTOCOL NUMBER: CCB-CRISIS-01  
PROTOCOL VERSION DATE: 01MAY2020

Page 28 of 55

## 8.6 Treatment Compliance

Compliance will be assessed by reviewing the subject's EHR and other study records as appropriate.

## 8.7 Storage, Stability, Labeling and Packaging

### 8.7.1 Storage and Stability

The study drug is stored at room temperature. Stability testing is ongoing.

### 8.7.2 Labeling and Packaging

Each brequinar bottle/dispensing container for subject use will be labeled with at least the following information:

#### **For Clinical Trial Use Only**

Study Number: CCB-CRISIS-01  
Contents: Brequinar 100 mg capsules  
For oral use only. Take with approximately 8 ounces water.  
Subject Number: XX-XXXX  
Treatment Duration: As directed  
Clinical Batch Number: XXXXXXXX  
Expiration Date: TBD  
Storage: Store at controlled room temperature  
Study Sponsor: Clear Creek Bio, Inc., [name]  
Caution: New Drug – Limited by US Federal Law to Investigational Use  
Only. To be used by Qualified Investigators only.

### 8.7.3 Blinding and Randomization

The trial will be conducted in an open-label manner with random assignment to standard of care or standard of care plus brequinar. The brequinar capsules will be provided to each participating institution in bulk to be dispensed by the institution's pharmacist for each subject. Randomization assignments will be provided by the sponsor.

### 8.7.4 Unblinding/Expectedness

It is not necessary to break the blind for this open label study as the treatment will be known for each subject.

Expectedness will be determined by establishing whether the adverse event is among those identified in the protocol and the brequinar IB or are commonly associated with COVID-19 or similar severe viral illnesses and their complications.

PROTOCOL NUMBER: CCB-CRISIS-01  
PROTOCOL VERSION DATE: 01MAY2020

Page 29 of 55

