#### 8.2.1 Safety/Tolerability

Safety/tolerability is assessed for each subject at each study visit using the Common Terminology Criteria for Adverse Events v4.03 (CTCAE).

Adverse events (AEs) commonly observed in patients treated with brequinar are provided in the Investigator's Brochure (IB) and include thrombocytopenia, nausea, anemia, diarrhea, vomiting, leukopenia, stomatitis, rash, granulocytopenia, fatigue, and infection. In a study of 209 subjects treated once-weekly (DuP 785-012, see Brequinar IB [5]), the deaths of three patients were attributed to study drug toxicity (two to hemorrhage, one following acute renal failure). Severe toxicities grades (Grades 3 to 4) which typically led to discontinuation in this study included hematologic toxicities (anemia, thrombocytopenia, leukopenia, granulocytopenia), digestive system toxicity (nausea, vomiting, stomatitis, others including gastric hemorrhage) and mucositis.

In three oncology studies (Study 785-001 [16], 785-003 [17], and 785-005 [18]) with five consecutive days of intravenous (IV) brequinar dosing and 168 subjects, there were no toxic deaths. For subjects from these three studies who were treated with a dose of 100 mg or below (as will be dosed in CCB-CRISIS-01), AEs through 21 days showed that 2 of 39 subjects (5.1%) had a severe (Grades 3 or 4) AE related to study drug (1 subject each with hyperbilirubinemia and hyperglycemia), and no subjects discontinued from the study due to a study drug-related AE. The few study drug related AEs through 21 days at or below the 100 mg dose from these three studies included 2 subjects each with nausea, vomiting, and creatinine elevated and one subject each with thrombocytopenia and diarrhea. When only studies with oral dosing were considered at this dose level (Studies 785-022 [19], 785-031 [20], and 785-034 [21]), the study drug related AEs through 21 days (each observed in one subject only) included diarrhea, headache, nausea, pruritus, abdominal pain, anorexia, chest pain, dry mouth, fatigue, keratosis, stomatitis, and vomiting. See brequinar IB (5).

PROTOCOL NUMBER: CCB-CRISIS-01  
PROTOCOL VERSION DATE: 01MAY2020

Page 27 of 55

In most instances, brequinar-related toxicities were transient, clinically manageable and reversible upon discontinuation of brequinar treatment. Any of these events reported with brequinar use can be serious in nature and may result in death.

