## **10.2 Classification of Severity**

The descriptions and grading scales found in the revised NCI CTCAE version 4.03 will be utilized for AE reporting. All appropriate treatment areas should have access to a copy of the criteria. The CTCAE version 4.03. A copy of the CTCAE version 4.03 can be downloaded from the Cancer Therapy Evaluation Program (CTEP) web site [http://ctep.cancer.gov/protocolDevelopment/electronic\\_applications/ctc.htm](http://ctep.cancer.gov/protocolDevelopment/electronic_applications/ctc.htm).

AEs that are expected are subject to expedited reporting only if the adverse event varies in nature, intensity or frequency from the expected toxicity information that is provided in the Investigator Brochure.

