## **10.3 Serious Adverse Event (SAE) Reporting**

The regulatory definition of an SAE is any untoward medical occurrence or effect that at any dose:

- results in death;
- is life threatening (at the time of the event);
- requires in-patient hospitalization or prolongation of existing hospitalization;
- results in persistent or significant disability / incapacity, or
- is a congenital anomaly / birth defect;
- all other events that are considered medically serious by the Investigator.

**Disability** is defined as a substantial disruption of a person’s ability to conduct normal life functions.

**A life-threatening adverse event** is one that places the patient/subject, in the view of the Investigator, at immediate risk of death from the event as it occurred. It does not include an event that, had it occurred in a more severe form, might have caused death.

**An unexpected adverse event** is any adverse drug event, the nature or severity of which is not consistent with the applicable product information (e.g. IB for an unauthorized investigational product or summary of product characteristics for an authorized product).

Enter only one event as the reason for the SAE on the SAE form. Other non-serious events which did not directly result in the SAE should be detailed in the description section on the SAE form and listed separately as AEs if necessary. For fatal SAEs, report the cause of death as an SAE with a fatal outcome rather than reporting death as the SAE term.

Note that hospitalizations for the following reasons should not be reported as SAEs:

PROTOCOL NUMBER: CCB-CRISIS-01  
PROTOCOL VERSION DATE: 01MAY2020

Page 40 of 55

The Sponsor is to ensure that all relevant information about **fatal or life-threatening** SUSARs are appropriately recorded and reported to the concerned Regulatory Authority and to the concerned IRB(s) within seven (7) calendar days of the date of first report to the Medical Monitor/Sponsor. Follow-up information is to be subsequently communicated to the relevant Regulatory Authority within an additional eight calendar days.

All other SUSARs are to be reported to the Regulatory Authority and to the IRB(s) concerned as soon as possible within a maximum of fifteen calendar days of first knowledge by the Medical Monitor/Sponsor.

The Medical Monitor/Sponsor or designee must also inform all Investigators studying the investigational medicinal product about SUSARs and ensure that all IRBs have been notified.

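### Section 8.7.4 decides expectedness by listing or by association with COVID-19, while Sections 10.2 and 10.3 test events against the product information; the rules need reconciling

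*Protocol*

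**What the plan says.** All of the following is from the version dated 01MAY2020.

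- **Section 8.7.4, first route.** "Expectedness will be determined by establishing whether the adverse event is among those identified in the protocol and the brequinar IB".
- **Section 8.7.4, second route.** The same sentence continues: "or are commonly associated with COVID-19 or similar severe viral illnesses and their complications".
- **Section 10.3.** An unexpected adverse event "is any adverse drug event, the nature or severity of which is not consistent with the applicable product information". The example given for an unauthorised product is the IB.
- **Section 10.2.** An expected event is subject to "expedited reporting only if the adverse event varies in nature, intensity or frequency from the expected toxicity information" given in the IB.
- **Section 8.2.1.** It names the adverse events commonly seen with brequinar, refers to the IB for them, and includes infection and rash. It also says: "Any of these events reported with brequinar use can be serious in nature and may result in death".
- **Section 3.2.** It names sepsis, acute kidney injury and cardiac injury among the complications of severe COVID-19.

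**The concern.** Expectedness is one of the two conditions for expedited reporting of a serious adverse reaction; relatedness to the drug is the other. It should ask one question: is this reaction, in kind and in degree, already described for this product? Section 8.7.4 asks something else, in two respects.

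First, it looks only for the event among those identified. Once a term is there, any grade of it satisfies the wording.

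Second, it admits what the disease does as evidence of what is expected from the drug. That mixes expectedness with causality. Whether COVID-19 explains an event belongs to the causality assessment, and the guidance in Section 10.1 already puts it there. If the event has been judged drug-related despite COVID-19, the fact that COVID-19 can also cause it does not make it a known reaction to brequinar.

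The practical risk is inconsistent handling. Two assessors who each follow a section of the protocol could classify the same related serious event differently, and only one of the classifications leads to expedited reporting as an unexpected reaction.

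**Working it through.** The protocol states no figure here and no arithmetic applies. The check is to set the rules side by side and pass two kinds of event through them.

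| | Section 8.7.4 | Section 10.3 | Section 10.2 |
|---|---|---|---|
| Reference | Protocol and IB, or common association with COVID-19 or similar illness | Applicable product information (IB) | IB |
| Criterion | Event is listed or associated | Nature or severity not consistent | Nature, intensity or frequency differs |
| Severity counts? | No | Yes | Yes |
| Disease association counts? | Yes | No | No |
| Dose named as a criterion? | No | No | No |

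**Event A: a drug-related serious event that is a common complication of COVID-19.** Take cardiac injury, which Section 3.2 names as a complication and which is not in the list of common brequinar events in Section 8.2.1.

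1. Section 8.7.4: the second route is met, so the event is expected.
2. Section 10.3: COVID-19 is not a reference. If the IB does not describe the event, it is unexpected.
3. The two sections disagree on that assumption about the IB.

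Sepsis is a similar case. Section 3.2 names it as a complication, and infection is a listed brequinar event in Section 8.2.1, so either route of Section 8.7.4 could be argued. Under Section 10.3 the assessor must still ask whether sepsis, at that severity, is consistent with the IB.

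**Event B: a listed toxicity at a severity that the IB does not describe.** Take rash, which Section 8.2.1 lists among the common events without a grade.

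1. Section 8.7.4: the term is identified in the protocol and, according to Section 8.2.1, in the IB. The event is expected at any grade. Reading *and* strictly, so that both documents must list it, does not alter this.
2. Section 10.3: if the IB describes rash only at lower grades, a life-threatening rash is unexpected on severity.
3. The two sections disagree, again on an assumption about the IB.

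For event B the protocol's role as a reference adds to the difficulty. The sentence in Section 8.2.1 that any of the reported events may result in death could be read, under Section 8.7.4, as identifying every listed term at fatal severity. Under Section 10.3 only what the product information says would count.

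**Which rule governs?** Section 8.7.4 is phrased as the operative instruction and Section 10.3 as a definition. Neither refers to the other. The opening of Section 10.4, where the protocol would define a SUSAR, is not in the text available for this version. In the version dated 10APR2020, Section 10.4 takes unexpected to mean not previously described in the IB, and gives the judgement to the Medical Monitor and the site Investigator. That is a further wording: the IB alone, with no mention of severity or of COVID-19.

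**The case against.** The strongest reply is that the protocol, read as a whole, does take severity into account. Section 8.7.4 can be taken to name the sources and Section 10.3 to set the matching test. Section 10.2 is a safety net as well: an event called expected still goes to expedited reporting if it differs from the IB in nature, intensity or frequency, and applied carefully that should recover both example events. Section 10.6 also provides weekly hematology review by the Medical Monitor, periodic DSMB review, and suspension of enrollment if hematologic rate or severity appears worse than expected. None of that depends on SUSAR status.

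Much of this stands. It is why the consequence is that reporting *could* be affected, not that it would fail. It does not remove the contradiction. The COVID-19 route in Section 8.7.4 has no counterpart in Section 10.3, so the two cannot be merged simply by treating one as sources and the other as test. Relying on Section 10.2 also means calling an event expected and then reporting it because it was not, which is a poor rule to give to sites.

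A reader might go further and infer that a fatal bleed at 100 mg would be expected and so would not be a SUSAR. The documents do not support that. Section 8.2.1 reports deaths "attributed to study drug toxicity (two to hemorrhage, one following acute renal failure") in a once-weekly oncology study, with reference to the IB. If the IB describes fatal hemorrhage, the event might be expected under a severity test too, so the example does not separate the rules. Section 10.2 could still require expedited reporting, and neither the IB nor the opening of Section 10.4 is available. The count of 3 deaths in 209 subjects has no bearing on how an event is classified. Nor does any of the three sections make dose a criterion, so a complaint that dose is ignored would be a preference and not a contradiction.

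Finally, later versions exist. Their contents pages show the section renumbered 8.8.4, but their text is not available, so the wording may already have changed.

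**Conclusion.** The contradiction is established in the version dated 01MAY2020. Section 8.7.4 tests listing or disease association without severity; Section 10.3 tests nature or severity against product information; Section 10.2 adds frequency. The point should be corrected: it concerns safety reporting and costs little to put right.

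Its size cannot be expressed as a number. It covers any drug-related serious event that is either a common complication of COVID-19 or a listed brequinar toxicity beyond the severity described in the IB. How many events that would be depends on the content of the IB.

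The conclusion rests on two assumptions: that the IB does not describe every COVID-19 complication, or every listed toxicity at every severity, as a brequinar reaction; and that the unseen opening of Section 10.4 does not say which test prevails. If Section 10.4 does settle precedence, the finding reduces to removing a misleading paragraph from Section 8.7.4. Nothing here shows that a particular event would go unreported.

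**What to change.** Reconcile the passages as follows.

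1. Replace the rule in Section 8.7.4 by the Section 10.3 definition, or by a cross-reference to it: an event is expected only if both its nature and its severity are consistent with the IB, which is the single reference document.
2. Remove listing in the protocol, and association with COVID-19 or similar illness, as sources of expectedness for the drug. COVID-19 can still inform causality under Section 10.1.
3. State how Section 10.2 relates to this definition, so that intensity and frequency against the IB are not read as a separate test.
4. Check that Section 10.4, and Section 8.8.4 in the later versions, use the same test.

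The cost is rewording one paragraph and checking the related sections. The downside is possibly a few more expedited reports.

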### **8.7.5 Study Drug Accountability**

The study drug provided is for use only as directed in this protocol.

The Investigator must keep a record of all study medication received, used and discarded. It must be clear from the records whether the subject received study medication or was assigned to standard of care. Adequate drug is to be dispensed for the number of subjects expected to be treated at each institution.

The pharmacist/staff member responsible for drug accountability is to document the date and time of dispensing and for what subject the study drug was intended (i.e., record subject initials and birth date or other unique identifier). A pharmacy manual will be provided by the Sponsor.

At the end of the study, any unused study drug will be returned to the Sponsor for destruction or may be destroyed locally; disposition of study drug will be documented.

The Sponsor will be permitted access to the trial supplies at any time within usual business hours and with appropriate notice during or after completion of the study to perform drug accountability reconciliation.

### **8.8 Prohibited Medications**

Treatment is prohibited with another DHODH inhibitor (e.g., leflunomide and teriflunomide), tacrolimus, sirolimus, or pre-existing prednisone at higher than 20 mg daily (ongoing or within 2 weeks of study entry).

### **8.9 Study Adjustments Due to COVID-19**

Due to the highly contagious nature of COVID-19, multiple adjustments and revised procedures are rapidly evolving regarding clinical trial management and study conduct. Reasonable procedures implemented by study staff to avoid spreading this disease are acceptable to Clear Creek with written permission. Examples include but are not limited to e-consent, telephone consent and study visits conducted by telephone or other digital media. Study information is to be collected from the EHR as much as possible such as NEWS2 Assessments, height, weight, hematology/chemistry, from Progress Notes for AEs, and from medication records for new or changed concomitant medications. Visits to an outpatient laboratory post hospital discharge may be required if subjects are not able or permitted to return for follow up study visits.

## **9 CONDUCT OF THE TRIAL**

### **9.1 Ethical and Regulatory Considerations**

The trial will be performed in accordance with the Declaration of Helsinki (1964) as revised in Tokyo (1975), Venice (1983), Hong Kong (1989), South Africa (1996), Scotland (2000, Note of Clarification 2002 & 2004) and Seoul 2008 (Appendix A), and Fortaleza (Brazil) (2013), and with the International Council on Harmonization (ICH) Tripartite Guideline on Good Clinical Practice (CPMP/ICH/135/95, Jan.97) and United States (US) FDA Regulations.

### **9.2 Informed Consent**

The principles of informed consent in the current edition of the Declaration of Helsinki must be implemented in each clinical study before protocol-specified procedures are carried out. Informed consent must be obtained in accordance with US Code of Federal Regulations (21 CFR Part 50), the FDA Guidance on Conduct of Clinical Trials of Medical Products during the COVID-19 Public Health Emergency (March 2020, Updated April 16, 2020), as well as local and national regulations. Information should be given in both oral and written form whenever possible and deemed appropriate by the Institutional Review Board (IRB). Subjects and their relatives, if necessary, must be given ample opportunity to inquire about details of the study.

The Investigator or qualified designated person will verbally inform subjects as to the nature, expected duration and purpose of the trial, the administration of the Investigational Product (IP), and the hazards involved, as well as the potential benefits that may come from treatment with this IP. The trial procedures will be explained in lay language and any questions will be answered. The subjects will be given an IRB-approved consent form. The subjects will be given appropriate time to consider their participation in the trial and have any questions answered prior to signing the consent form. If a subject agrees to participate, he/she will sign and date an informed consent form and be provided with a copy of the signed consent. All subjects who sign an informed consent form are to be recorded on the applicable screening log. If the subject is unable to consent for any reason, a designated family member or healthcare power of attorney or other person may consent per institutional policy.

The subject will be informed that his/her medical records will be subject to review by the Sponsor, Sponsor's representatives, and possibly by a representative of the FDA and other relevant regulatory authorities. Subjects will be informed that they are free to refuse participation in this clinical investigation, and if they should participate, it will be made clear to them that they may withdraw from the trial at any time without prejudicing further medical care they may require. The subject will receive a copy of the consent form as well as an information sheet about the trial.

Signed written informed consent must be obtained from every subject prior to any study-specific procedures. Standard procedures carried out prior to signing the informed consent but within the time constraints of the protocol may be used for baseline evaluation; they need not be repeated. An original signed informed consent form will be subject to review by the Sponsor; a copy will be given to the subject and a copy will be filed with the subject's medical notes.

Note that informed consent procedures have been affected by COVID-19, and the study staff may use any consent method that has been approved by the IRB (e.g., phone consent, verbal consent

PROTOCOL NUMBER: CCB-CRISIS-01  
PROTOCOL VERSION DATE: 01MAY2020

Page 31 of 55

with witness, e-consent, etc.) of the local institution. In-person consent, written consent signatures and providing hard copies to the subject are examples of procedures that may be foregone under these circumstances.

The study should be discussed with the potential participant only after an initial review of his/her clinical status and appropriateness for participation have been evaluated to determine if he/she meets the subject selection criteria.

A sample subject information sheet and consent form are available from Clear Creek. The final version at each institution may differ depending on institutional requirements and standard formats. This protocol will not be amended for site specific changes.

